Department of Urology
[name]
[name]
[contact]
Email: [contact]

Sub-Investigator:

[name]
Professor
Department of Pathology
[name]
[name]
[contact]
Email: [contact]

Sub-Investigator:

[name]
Associate Professor
Department of Radiology
[name]
[name]
[contact]
Email: [contact]

Sub-Investigator:

[name]
Associate Professor
Department of Radiation Oncology
[name]
[name]
[contact]
Email: [contact]

Sub-Investigator:

[name]
Professor
Department of Urologic Surgery
[name]
[name]
[contact]
Email: [contact]

Sub-Investigator:

[name]
Professor
Department of Radiation Oncology
[name]
[name]
[contact]
Email: [contact]

Sub-Investigator:

[name]
Assistant Professor
Department of Radiation Oncology
[name]
[name]
[contact]
Email: [contact]

Biostatistician:

[name]
Associate Professor
Institute for Health and Society
Division of Biostatistics
[name]
[name]

[contact]
Email: [contact]

Funder:
MCW Cancer Center

Drug supply
CTI BioPharma

[figure not shown]
PROTOCOL SUMMARY

Title	A Phase 2 Study of Pacritinib for the Biochemical Relapse after Definitive Treatment for Prostate Cancer
IND Sponsor	Investigator-Sponsor
Principal Investigator	[name]
Clinical Trial Phase	Phase 2
Study Population	Patients with histologically or cytologically confirmed prostate adenocarcinoma, status post definitive treatment and biochemical recurrence.
Primary Objectives	To determine the effect of pacritinib on the time to PSA progression in patients with biochemical relapse of prostate cancer (defined as the length of time that a given subject will be alive and free from PSA progression per PCWG3 guidelines).
Secondary Objectives	
 1. To evaluate the absolute PSA nadir as a result of treatment. 2. To determine the time to PSA nadir from the start of treatment. 3. To determine the time to subsequent antineoplastic therapy 4. To determine the effect of investigational treatment on testosterone levels 5. To determine the safety and toxicities of the study drug.
Explorative Objectives	
 1. To determine the effect of study drug on comprehensive geriatric assessment domains. 2. To determine the effect of the study drug on short-term and long-term health-related quality of life (HRQOL) 3. To evaluate if positive status for Stat5 activation in the paraffin-embedded tissue sections of the most recent biopsy specimen has a trend to predict biochemical response to pacritinib treatment
Study Design	Single-arm, open-label study.
Study Agent	Pacritinib 200 mg BID.
Number of Subjects	N= 46. The first cohort of the study will enroll 10 patients. Enrollment to the second cohort(n=36) would be dependent on the response noted in the first cohort and funding.
Estimated Time to Complete Enrollment:	Approximately 12 months for the first 10 patients and 36 months for total study.

Inclusion criteria	
 ▪ Histologically or cytologically confirmed prostate adenocarcinoma. ▪ Prior radical prostatectomy or definitive radiation therapy. ▪ Biochemically recurrent prostate cancer with PSA doubling time \leq 9 months at the time of study entry. ▪ Prior adjuvant or salvage radiation or not a candidate for radiation based upon clinical assessment of disease characteristics and patient comorbidities. ▪ Screening PSA $>$ 0.5 ng/mL. ▪ No definitive evidence of metastases on screening imaging per the judgment of the investigator. Pelvic lymph nodes measuring 1.5 cm or less in short axis diameter are allowed. ▪ Screening serum testosterone $>$ 50 ng/dL. ▪ Eastern Cooperative Oncology Group (ECOG) Performance Status grade 0-1 or Karnofsky Performance Status \geq 70. ▪ Age \geq 18 years. ▪ Absolute neutrophil count \geq 500/ μL, ▪ Agrees to use a condom (even men with vasectomies) and another effective method of birth control if he is having sex with a woman of childbearing potential. ▪ Adequate organ function. ▪ Left ventricular cardiac ejection fraction of \geq 50% by echocardiogram or multigated acquisition scan. ▪ Adequate coagulation defined by prothrombin time/international normalized ratio and partial thromboplastin time \leq 1.5x ULN.
Exclusion criteria	
 ▪ Prior systemic treatment with androgen deprivation therapy and/or first-generation anti-androgen (e.g. bicalutamide, nilutamide, flutamide) for biochemically recurrent prostate cancer (prior systemic treatment in the neoadjuvant, setting with definitive and/or salvage RT allowed as long as the interval between completion of systemic treatment and the start of pacritinib \geq12 months) ▪ Prior treatment with CYP17 inhibitor (e.g., ketoconazole, abiraterone acetate, galeterone) or next-generation androgen receptor antagonist including apalutamide or enzalutamide. ▪ Prior chemotherapy for prostate cancer ▪ Use of 5-alpha reductase inhibitor within 42 days before randomization. ▪ Use of investigational agent within 28 days before randomization. ▪ Use of other prohibited medications within seven days before Cycle 1 Day 1 on study. ▪ Prior bilateral orchiectomy. ▪ Uncontrolled hypertension. ▪ Gastrointestinal disorder affecting absorption or the ability to swallow tablets. ▪ Baseline severe hepatic impairment (Child-Pugh Class B & C) ▪ Intercurrent illness that is not controlled, such as active infection, psychiatric illness/social situations that would limit compliance with study requirements.

	
 ▪ Any chronic medical condition requiring a higher dose of corticosteroid than the equivalent of 10-mg prednisone /prednisolone per day.
Statistics	
A two-stage design based on the methods of Huang et al (2010) will be used. The null hypothesis that the median PSA-progression-free survival is six months will be tested against a one-sided alternative by for the six-month PSA-progression-free survival probability exceeding 50%. The study is designed to have 80% power to obtain a result significant at a one-sided 10% level if the experimental treatment has a six-month PSA-progression-free probability of 66%, which corresponds to a median of 10 months if the time to PSA progression is exponentially distributed.
 
The design is based on a modification of a binomial two-stage design that allows the incorporation of data from subjects with less than six months of follow-up at the interim analysis. The study will enroll up to 46 subjects with an interim analysis performed when 10 patients have been treated and followed for six months.

Pacritinib Dosage Modifications	Pacritinib dosage may be interrupted or modified for pacritinib-related hematologic toxicities, hemorrhage, severe infections, cardiac toxicities (including QTcF interval prolongation and reduction in ejection fraction), diarrhea, and other pacritinib-related nonhematologic toxicities. Pacritinib dosage may also be held for invasive procedures or at the discretion of the investigator. Refer to Section 5.2 for pacritinib dosage management guidelines.
Safety	Safety and tolerability will be assessed primarily by the incidence, severity, and change from baseline in safety parameters, such as treatment-emergent AEs (TEAEs; including SAEs), laboratory values, cardiac assessments, and vital signs.

STUDY SCHEMA

RT-radiation therapy
BID- twice a day
ADT-androgen deprivation therapy
LN-lymph node
DT-doubling time

STUDY CALENDAR

Study Assessments	Screening ¹		Cycle 1 ²		Cycle 2		Cycle 3		Cycle 4		Cycle 5		Cycle 6 and beyond (Treatment till progression)		End of treatment ¹ (EOT) visit ± 7 ⁴	Follow-up (2 years) ³
	Day - 30 to -1	Day - 30	Each Cycle (28 days)												30-day post-last dose Safety Visit (±7 days)	Every 6 months post EOT visit (±21 days)
Informed consent	X				1	15±3	±3	±3	±3	±3	±3	±3	Every 2 months (± 7 days)	Progression + - 7 ⁴		
Medical History ¹¹	X															
AE reporting			Recorded from Day 1 through 30 days after the last dose of study drug.													
Concomitant Medications			Recorded from the signing of the ICF through 30 days after the last dose of study drug.													
Physical Exam	X	X			X	X	X	X	X	X	X	X	X	X	X	X
Vital Signs ⁴	X	X			X	X	X	X	X	X	X	X	X	X	X	X
ECOG Performance Status	X	X			X	X	X	X	X	X	X	X	X	X	X	X
12-lead ECG ⁵	X	X				X				X		X	X ⁶			
Transthoracic echocardiogram (TTE) ⁶	X					X				X		X	X ⁶			
Comprehensive Geriatric Assessment	X										X					
Tissue for STAT 5 analysis ¹⁰	X															
Serum PSA	X	X				X	X	X	X	X	X	X	X	X	X	X
Serum Testosterone	X															
CBC w/ Diff	X	X			X	X	X	X	X	X	X	X	X	X	X	X
Blood Chemistry ⁸	X	X			X	X	X	X	X	X	X	X	X	X	X	X

Study Assessments	Screening		Cycle 1 ²	Cycle 2	Cycle 3	Cycle 4	Cycle 5	Cycle 6 and beyond (Treatment till progression)	End of treatment ¹ ² (EOT) visit	Follow-up (2 years) ³
	Each Cycle (28 days)		(in Days)		Every 2 months (± 7 days)		Every 2 months (± 7 days)	30-day post-last dose Safety Visit (±7 days)	Every 6 months post EOT visit (±21days)	
	Day -30 to -1	1	15±3	±3	±3	±3	±3	Progression +/ -		
Coagulation (PT/PTT) and Hb A1C	X									
Research blood draw	X		X		X				X	
CT of Abdomen and Pelvis. /CT urogram/MRI abdomen and pelvis/PET ^{9, 13,15}	X				X				X	
Bone scan ^{9, 13,15}	X				X				X	
Chest Imaging ^{9,15}	X								X	
Pacritinib dispense	X ⁷		X ⁷	X	X	X ⁷	X ⁷		X	
Patient-reported outcome instrument: - FACT-P	X					X				

1. All screening procedures must occur within 30 days prior to treatment initiation.
2. Day 1 assessments are required to be performed prior to initiation of study treatment and can be performed up to 24 hours prior to initiation of study treatment. Study days are to be counted based on the start of treatment.
3. If a subject has disease progression or subject withdrawal, then they will be followed as per follow-up requirements. Patients will be in follow up for 2 years from EOT visit.
4. Vital signs include systolic and diastolic blood pressure, pulse, respiratory rate, temperature, and body weight.
5. A 12-lead ECG (collected in triplicate), including QTcF, will be performed at Screening, and then predose at C1D1, C2D1,, C5D1, C7D1, and every four months (every other cycle/odd cycles) thereafter provided normal QTcF.. if QTc is prolonged, more frequent monitoring will be done after discussion with sponsor. For patients who have discontinued treatment, ECGs are to be performed at the End-of-Treatment Visit but are not otherwise required
6. TTE will be performed at screening, C2D1, C5D1, C8D1, and every six months thereafter (every 3 cycles) provided normal LVEF and no

clinical evidence of heart failure. Window for all TTEs is -14 days from Day 1 of the cycle it is due for.

7. On days when ECGs are to be obtained, Pacritinib will be administered in the clinic to facilitate the performance of pre-dose assessments
8. Serum chemistry values will include AL T/SGPT, AST/SGOT, alkaline phosphatase, bilirubin (total, direct, and indirect) creatinine, LDH, sodium, potassium, chloride, bicarbonate, calcium, phosphate, magnesium, BUN/urea, albumin, glucose, cholesterol (fasting not required), and uric acid. Serum chemistry results obtained from unscheduled visits should be entered into the electronic database.
9. Additional serum chemistry testing should be done as clinically indicated.
10. Unscheduled visits should include physical examination, laboratory tests, and radiographic evaluations as clinically indicated in the judgment of the investigator and these results must be entered into the clinical database (e.g., electronic data capture). Additional visits may be required for patients who have pacritinib dose modifications due to hematologic, cardiac, diarrhea, or other non-hematologic toxicities. Results of clinical laboratory assessments at unscheduled visits should be entered into the electronic database.
11. Core biopsy or surgical specimens from primary prostate cancer prior to administration of Jak2 inhibitor as well as other archive tissue (if available) will be used for study biomarker assessments. Tissue from surgical specimen will be preferred over core biopsy specimens when available. One hematoxylin and eosin slide and five unstained slides from formalin-fixed, paraffin-embedded pathology blocks with cancer will be reserved for study labs/biomarkers. If adequate tissue is not available, the patient would still qualify and be enrolled to the study.
12. Treatment duration is expected to be 2 years. Patients may continue drug beyond 2 years, if in the opinion of the treating physician, the patient is benefitting from treatment and benefits outweigh the risks of therapy.
13. imaging due at Cycle 4 has a 14-day window
14. If any of the required progression assessments have already been completed in the last 30 days, at the treating physician's discretion, they do not need to be repeated.
15. If PSMA/Axumin PET imaging is performed at baseline, other imaging is not required in addition to PET. Different modalities may be used at each imaging timepoint based on treating provider and insurance preference.

LIST OF ABBREVIATIONS

AE	Adverse Event
ALP	Alkaline Phosphatase
ALT	Alanine Aminotransferase
ANC	Absolute Neutrophil Count
AST	Aspartate Aminotransferase
AUC	Area Under the Curve
BUN	Blood Urea Nitrogen
CBC	Complete Blood Cell (Count)
CDK	Cyclin-Dependent Kinases
CQ	Chloroquine
CR	Complete Response
CRC	Clinical Research Coordinator
CRF	Case Report Form
CSF	Cerebral Spinal Fluid
CT	Computerized Tomography
CTCAE	Common Terminology Criteria for Adverse Events
CTL	Cytotoxic T Cell
CTO	Clinical Trials Office
DFS	Disease-Free Survival
DLT	Dose-Limiting Toxicity
DSMC	Data and Safety Monitoring Committee
DSMP	Data and Safety Monitoring Plan
ER	Estrogen Receptor
FDA	Food and Drug Administration
GCP	Good Clinical Practice

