4.6 Discontinuation of Study Treatment, Withdrawal, and Compliance

Treatment duration is 2 years. Patients may continue drug beyond two years if, in the opinion of the treating physician, the patient is benefitting from treatment and benefits outweigh any risks of therapy

Discontinuation from the study treatment does not mean discontinuation from the study. The subject will be considered in follow-up, study procedures should still be completed as indicated by the study protocol, and AEs/SAEs will continue to be reported according to this protocol.

In the absence of treatment delays due to adverse events, study treatment/intervention may continue until:

- Disease progression per PCWG3 guidelines
- General or specific changes in the subject's condition renders the subject unacceptable for further treatment in the investigator's judgment.
- An inter-current illness that prevents further treatment administration.
- The subject decides to withdraw from the study.
- The subject has significant noncompliance with the protocol (see below).
- Unacceptable adverse event(s) and/or dose level reduction beyond requirements as detailed in this protocol.
- The clinical need for concomitant therapy that is not permitted in the study.
- Subjects who sign the informed consent form, enroll and receive the study intervention, but subsequently withdraw, or are withdrawn or discontinued from the study will not be replaced.

Progression of disease

Progression of disease per PCWG3 is defined as one or more of the following:

PSA progression

Recognize that a favorable effect on PSA may be delayed for \geq 12 weeks, even for a cytotoxic drug. Monitor PSA by cycle but plan to continue through early rises for a minimum of 12 weeks unless other evidence of progression.

If there is a decline in PSA from baseline: record time from baseline to the first PSA increase that is $\geq 25\%$ and ≥ 2 ng/mL above the nadir, and which is confirmed by a second value ≥ 3 weeks later (i.e., a confirmed rising trend).

If there is no decline in PSA from baseline but stable PSA at 12 weeks: PSA progression will be defined as $\geq 25\%$ and ≥ 2 ng/mL from PSA at 12 weeks .

Radiographic progression

Radiographic progression will be assessed per RECIST 1.1. Any new unequivocal bone lesion is considered progression, except if that lesion appears in the first post-treatment scan; in that

case, document the event, continue treatment until two additional new lesions appear, and record both events.

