Bleeding: Pacritinib may increase the risk of bleeding. Reports of serious bleeding events, including life-threatening and fatal events, have been reported. These bleeding events were generally without lasting sequelae, although life-threatening and fatal events of hemorrhage, including intracranial hemorrhage, were observed more frequently in pacritinib-treated patients compared with BAT patients. Risk factors for bleeding with pacritinib may include prior bleeding events and anti-platelet and anti-coagulant medications in addition to severe thrombocytopenia. Concomitant use of drugs affecting hemostasis, such as aspirin and other antiplatelet agents, other anticoagulants, heparin, and thrombolytic agents, may increase the risk of bleeding. Refer to the protocol for guidance on dose modifications for pacritinib-related bleeding events.

Cardiac: QTc prolongation has been observed in patients treated with pacritinib. Prior to initiating treatment with pacritinib, patients should undergo an ECG to establish baseline QTc and an echocardiogram (or other appropriate methodology) to establish baseline left ventricular ejection fraction; patients should be monitored periodically for changes in their QTc. Pacritinib should not be used in patients with uncontrolled cardiac dysrhythmias, QTc prolongation >450 ms, or other factors that increase the risk for QT prolongation (e.g., heart failure, hypokalemia, hypomagnesemia, or a history of long QT interval syndrome). Caution should be used when co-administering other medicinal products with the potential to elongate QT interval. Ejection fraction should be monitored at baseline, after one month on treatment, after three and six months on treatment, and every six months thereafter; pacritinib dose should be modified if significantly reduced ejection fraction is detected. Additional ECG and ejection fraction assessments should be performed as clinically indicated. Refer to the protocol for guidance on dose modifications for pacritinib-related QTc prolongation.

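### The primary test reads PSA-progression-free survival at six months, but no scheduled PSA is tied to six months, on or off study drug

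*Combined protocol and SAP*

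**What the plan says.** **The test.** Section 2.4 makes six-month PSA-progression-free survival the primary endpoint. Section 8.4 compares its Kaplan-Meier estimate with 50% by a z-test at one-sided 10%. Section 8.3 calls the drug promising if 27 or more of 46 men are alive without PSA progression at six months, after a futility look at 10 men. Six months is not defined in days or cycles.

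**On-treatment PSA.** The calendar header gives "Each Cycle (28 days" as the cycle length. From Cycle 6 visits are "Every 2 months (± 7 days", with no stated starting point. Section 4.6 says "Monitor PSA by cycle but plan to continue through early rises for a minimum of 12 weeks". Footnote 2 says "Study days are to be counted based on the start of treatment", but does not apply this to the two-monthly visits.

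**Cycle length.** Footnote 5 (ECG) reads "C5D1, C7D1, and every four months (every other cycle/odd cycles) thereafter" and footnote 6 (echocardiogram) reads "C8D1, and every six months thereafter (every 3 cycles". Both imply two-month cycles. Section 7.7 asks for ejection fraction "after three and six months on treatment, and every six months thereafter".

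**Off-treatment PSA.** The calendar has an end-of-treatment (EOT) visit 30 days after the last dose (±7 days), then visits every six months counted from EOT (±21 days).

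**Dating and censoring.** For a man whose PSA has declined, Section 4.6 says to "record time from baseline to the first PSA increase" that meets the threshold and is later confirmed. Section 8.10 censors men with a missing primary outcome when last known alive and progression-free. Neither 8.4 nor 8.10 mentions new antineoplastic therapy. Section 3.1 makes starting it a reason to end study treatment, and Section 4.6 continues study procedures after treatment stops.

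**The concern.** A Kaplan-Meier value at one time point can only reflect what was seen by the last draw on or before that time. A man who progresses between that draw and six months is first seen to have progressed later, is dated later, and counts as progression-free at six months. In a single arm tested against a fixed number, no control group shares this delay, so it goes straight into the result and favours the drug. A missing draw cannot be created at the analysis stage.

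Men who stop drug early without progression have a wider gap. If they also start new therapy, a PSA lowered by that therapy could later be read as freedom from progression. The protocol foresees such switches: Section 1.1 calls intermittent androgen deprivation the standard of care for biochemical relapse, and Section 2.5 makes time to next therapy a secondary endpoint.

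**Working it through.** **1. The plan's own figures.** Exact two-stage binomial (continue if 5 or more of 10; 36 further men):

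P(success) = Σ over x = 5 to 10 of P(X₁ = x | 10, p) × P(X₂ ≥ r − x | 36, p)

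- Early stop at p = 0.50: 37.7%. The stated 38% reproduces.
- r = 27: 13.3% at p = 0.50 and 83.1% at p = 0.66. The stated 10% and 80% do not reproduce.
- r = 28: 8.3% and 77.2%.
- With complete follow-up, 27/46 gives z = (0.587 − 0.5)/√(0.587 × 0.413/46) = 1.20, below 1.28; 28/46 gives 1.51. The z-test in 8.4 therefore needs 28.

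The mismatch between 27, 28 and 10% is a separate issue. Here 13.3% and 8.3% serve only as baselines.

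**2. Last on-treatment PSA by six months** (six months = 6 × 30.4375 = 182.6 days)

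- By 28-day cycle: C7D1 = 1 + 6 × 28 = day 169.
- Two months from C5D1: 113 + 61 = about day 174.
- Two months from C1D1: about day 183. This fits footnote 2, and Section 8.6, which counts three and six months from therapy initiation.

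Section 7.7 does not settle the cycle length. C8D1 is at 196/30.4375 = 6.4 months with 28-day cycles, or (141 + 2 × 61 − 1)/30.4375 = 8.6 months with two-month cycles from Cycle 6. The first is closer to six months, but C5D1 is at 112/30.4375 = 3.7 months against the stated three, so the text is too loose to date cycles.

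**3. Apparent null rate.** Assumptions: exponential times, true median six months, 50% null meaning true progression time, progression dated at the draw. Then the rate read at six months is S(d) = 0.5^(d/182.6), with d the day of the last draw. (Counting elapsed days instead, 168 for day 169, gives 52.9% rather than 52.7%.)

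| Last draw | Rate read | P(≥27 of 46) | P(≥28 of 46) |
|---|---|---|---|
| Six months exactly | 50.0% | 13.3% | 8.3% |
| About day 174 | 51.7% | 18.6% | 12.3% |
| Day 169 | 52.7% | 22.3% | 15.2% |

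The increase is 5.3 or 9.0 points with 27, and 4.0 or 6.9 points with 28.

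**4. The ±7-day window if visits run from C1D1.** A draw at day 183 reads 49.9%. Suppose a share f of draws falls after day 183, actual dates are used and the previous draw was day 141 (S = 58.6%). The rate is (1 − f) × 0.499 + f × 0.586. For f = 10% it is 50.8% and P(≥27) is 16%; for f = 25% it is 52.1% and 20%. The shares are assumptions. Dating at the nominal day returns 49.9% and 13%.

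**5. Off treatment.** Last dose on day D: PSA at about D + 30, next at about D + 30 + 183 = D + 213. D + 30 = 183 gives D = 153, so a man who stops earlier has his last scheduled PSA before six months. Using both windows, the earliest next visit is D + 23 + 162 = D + 185, which is after day 183 for any D. A man stopping on day 60 is drawn at about days 90 and 273.

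**6. New therapy.** The documents give no switching rate. As an assumption only, let 5% of men switch before six months, unrelated to their progression. Counting all as free reads 0.5 × 0.95 + 0.05 = 52.5%, with P(≥27) = 22%. Counting all as events reads 0.5 × 0.95 = 47.5%, with 7%.

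**The case against.** The strongest reply is that PSA progression is by definition seen at a draw. If the six-month median behind the 50% came from a trial with similar visits, the delay is already in the benchmark and most of the bias goes. The documents do not say how the benchmark was observed, so this limits the size without removing the gap. The C1D1 reading also has textual support, and under it almost nothing is lost apart from the window. That stands too, but the protocol never states it, and it does nothing for men off drug.

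The calendar's columns are hard to align in the public copy, footnotes 5 and 6 concern ECG and echocardiogram rather than PSA, and unscheduled results may be entered. These points weaken inference from the table. They do not supply a starting point or a six-month draw.

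A reader might infer three stronger things:

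- *That there may be no PSA between day 141 and about day 200, so that the null rate reads 58.6% and is rejected half the time.* The calendar alone permits this, but by-cycle monitoring in Section 4.6 fits it poorly, and the finding does not rest on it.
- *That visit timing produces the whole 22%.* It does not: 13.3 points come from the 27-of-46 rule.
- *That the plan counts PSA after new therapy as success.* It is silent. The direction of any bias depends on the rule chosen, and censoring at the switch can itself bias upward if men switch because PSA is rising.

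**Conclusion.** The point holds. The primary endpoint is tied to six months and no PSA is. On treatment, the effect under the day-169 and day-174 readings is 1.7 to 2.7 percentage points on the null rate, adding about 5 to 9 points to the chance of reaching 27 of 46, or 4 to 7 points for 28. This rests on exponential times, a true six-month median and a null that refers to true progression time. It is near zero, apart from the ±7-day window, if visits run from C1D1, and smaller if the benchmark used similar visits.

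Off treatment, the missing draw follows from the calendar under any on-treatment reading. Its effect depends on how many men stop drug before about day 153 without progression, which the documents do not give.

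The absent rule for PSA after new therapy is a real but secondary gap of unknown size. Overall this should be changed, because the remedy is cheap and cannot be applied after the visits have passed.

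**What to change.** **Main change.** Reconcile the cycle length and the starting point of the two-monthly visits across the calendar header, footnotes 5 and 6, and Section 4.6. Schedule a PSA at week 26 from C1D1 for every man without prior progression, on or off study drug, and state in 8.4 that progression seen there is dated at the nominal week-26 day.

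Moving the landmark to day 169 is not a good substitute. With a six-month median the rate there is 52.7%, so testing it against 50% keeps the same inflation, and a 10-month median gives about 68% rather than the planned 66%.

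**Secondary change.** State in 8.4 and 8.10 that PSA drawn after new antineoplastic therapy is not used to show freedom from progression. Choose either censoring at the start of that therapy or counting it as an event for the primary analysis, and report the other as a sensitivity analysis. Note that censoring is informative if men switch because PSA is rising, and say how such men enter the 27-of-46 count.

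**Cost.** With 28-day cycles the visits fall on days 169 and 197 and none is at week 26 (day 183), so one PSA visit moves by up to about two weeks or one PSA is added. Men who stop early give one extra PSA. Section 8 gains a few sentences. The start date of new therapy is already needed for a secondary endpoint.

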2.2 Secondary Objectives

1. To evaluate the absolute PSA nadir as a result of treatment which is expressed for each subject in the absolute value and as a percentage, change from baseline.
2. To determine the time to PSA nadir from the start of treatment. which is the lowest PSA on treatment.
3. To determine the time to next subsequent antineoplastic therapy.
4. To determine the effect of investigational treatment on testosterone levels which is assessed by the change of testosterone from baseline to cycle 4.
5. To determine the safety and toxicities of the study drug as assessed by CTCAE version 5.

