2.5 Secondary Endpoint(s)

1. Absolute PSA nadir.
2. Time to PSA nadir.
3. Time to next subsequent antineoplastic therapy.
4. Effect of investigational treatment on testosterone levels.
5. Safety and toxicities of the study drug.

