3.2 Study Completion

The study will reach study completion approximately 36 months from the time the study opens to accrual.

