8.5 Analysis of secondary endpoints

The PSA nadir values will be summarized with mean and standard deviation as absolute values and as percent change from baseline PSA value. The time to PSA nadir and time to subsequent antineoplastic therapy will be summarized using Kaplan-Meier (KM) curves. The median will be estimated using the inverse-KM method and shown with 95% confidence intervals. The change in testosterone levels from baseline to cycle 4 will be shown graphically using box-plots and reported with mean and standard deviation.

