8.10 Missing data

For all outcomes, summary statistics will include the count of missing and non-missing values. Patients with missing value for the primary outcome, PFS, will be censored at the time when last known to be alive and without progression. A similar approach will be used for other time-to-event outcomes, such as time to PSA nadir. Secondary outcomes requiring numeric values, such as geriatric assessments, PSA and testosterone levels will be analyzed among patients with non-missing values as required for each analysis (e.g., non-missing value at specific time point for cross-sectional analysis, and non-missing values at two time points for change analyses). The limitations of extensive missingness, if present, will be clearly noted in all reports and any related findings will be interpreted with caution.

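### Time to next antineoplastic therapy has no scheduled record beyond 30 days after the last dose, and the 36-month study length cannot hold the planned follow-up

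*Combined protocol and SAP*

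**What the plan says.** The endpoint is listed in Section 2.2 ("To determine the time to next subsequent antineoplastic therapy") and again in Section 2.5. Section 8.5 gives its analysis: "The time to PSA nadir and time to subsequent antineoplastic therapy will be summarized using Kaplan-Meier (KM) curves", with a median and 95% confidence interval. For censoring, Section 8.10 describes the rule for the primary outcome (last known alive and progression-free) and adds "A similar approach will be used for other time-to-event outcomes, such as time to PSA nadir". No rule is specific to this endpoint.

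On data collection, the concomitant-medication row of the Study Calendar reads "Recorded from the signing of the ICF through 30 days after the last dose of study drug". Follow-up visits are six-monthly, and footnote 3 states: "Patients will be in follow up for 2 years from EOT visit". The items legibly marked in that column are physical examination, vital signs, ECOG, PSA, blood count and chemistry. No row or footnote names subsequent therapy. Section 11.4 says that CRFs will document outcomes and that data are entered according to the calendar. Section 3.1 makes the start of a new prostate-cancer therapy a reason for ending study treatment.

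On duration, the enrolment-time row of the Protocol Summary says "Approximately 12 months for the first 10 patients and 36 months for total study". Section 3.2 says "The study will reach study completion approximately 36 months from the time the study opens to accrual". Section 8.3 puts the final analysis at the point when every subject has at least six months of follow-up and assumes 1.5 subjects per month. Section 4.6 and calendar footnote 12 plan about two years of treatment, possibly longer.

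**The concern.** Next therapy can start on pacritinib or soon after it stops, and such starts fall inside the recording window. It can also start later. Section 1.1 describes men who often have no symptoms and for whom early androgen deprivation has no clear survival benefit, so a delay after stopping is plausible. The dose-management rules in Section 5.2 also stop some men for toxicity without progression, and they may have no immediate reason to begin another drug.

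A man who starts new therapy two months after his last dose has no scheduled record of it. If he is censored when recording ends, he leaves the risk set shortly before his event, so the censoring is informative. If the Section 8.10 approach is instead read as censoring at last contact, he is counted as event-free at follow-up visits where nobody was required to ask about therapy. Both errors lengthen the estimated median. Start dates not collected during the trial may be impossible to recover after closure.

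The duration statements add a second problem: if month 36 were applied as a close, the follow-up in which later therapies could be recorded would be cut short.

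**Working it through.** **1. The stated 36 months.** It can be reached in two ways from the plan's own figures.
- As enrolment time: 10 subjects in 12 months, then the other 36 at 1.5 per month: 12 + 36/1.5 = 36.0 months.
- As enrolment plus six months at 1.5 per month throughout: 46/1.5 + 6 = 30.7 + 6 = 36.7 months.

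**2. What the follow-up needs.** The end-of-treatment visit is about one month after the last dose, and follow-up is 24 months from that visit.
- Shortest case, with the last subject enrolled at month 30.7 and stopping at once: 30.7 + 1 + 24 = 55.7 months.
- Longest planned case, with 24 months of treatment: 30.7 + 24 + 1 + 24 = about 80 months on the faster accrual, or 36 + 24 + 1 + 24 = 85 months on the slower.

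Neither reading of 36 months holds the two-year follow-up. On the enrolment reading it does not hold the six months required by Section 8.3 either: 36 + 6 = 42.

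**3. Events captured by the 30-day window.** Inputs from the plan: exponential time to progression with median m = 6 months (null) or 10 months (alternative), treatment to progression or 24 months, and a window w = 30/30.44 = 0.986 months after the last dose. The assumed input is an exponential gap from progression to next therapy with median g. For a man treated to progression, this is also the gap from last dose.

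The captured share is close to P(progression by 24 months) × P(gap ≤ w) = (1 − 2^(−24/m)) × (1 − 2^(−w/g)). A small addition covers men who stop at 24 months and then both progress and start therapy within the window.
- P(progression by 24 months): 0.938 at m = 6; 0.811 at m = 10.
- P(gap ≤ w): 0.495 at g = 1 month; 0.204 at g = 3 months.
- g = 1: 0.938 × 0.495 = 0.464 and 0.811 × 0.495 = 0.401; with the addition, 0.466 and 0.405.
- g = 3: 0.938 × 0.204 = 0.191 and 0.811 × 0.204 = 0.165; with the addition, 0.192 and 0.166.
- g = 0: 1 − 2^(−24.986/m) = 0.944 and 0.823.

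**4. Range of results.** Percentage of all next-therapy events captured. In each cell the lower figure is for m = 10 and the higher for m = 6. The month-36 columns come from simulation with 10 subjects entering uniformly over months 0–12 and 36 over months 12–36.

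| Median gap (assumed) | 30-day window, no early close | 30-day window, close at month 36 | New therapy recorded at follow-up visits, close at month 36 | Recorded for full two-year follow-up |
|---|---|---|---|---|
| 0 | 82–94 | 58–72 | 59–73 | 97–100 |
| 1 month | 40–47 | 28–35 | 55–68 | 96–100 |
| 3 months | 17–19 | 12–14 | 47–60 | 95–99 |
| 6 months | 9–10 | 6–8 | 38–49 | 89–93 |
| 12 months | 5 | 3–4 | 27–34 | 71–75 |

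With no gap, the window loses little. From a median gap of about one month upward it loses more than half of the events, and a month-36 close would be a further loss.

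**The case against.** The quoted row is a concomitant-medication window, not a limit on outcome collection. Section 11.4 says that CRFs will document outcomes, Section 4.6 keeps men in the study after treatment stops, and Section 4.7 refers to a follow-up tab and eCRF. The calendar mainly lists procedures: death counts toward the primary endpoint and has no row either. The calendar's columns are also shifted in the text as read, so its follow-up entries are partly a reconstruction.

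This stands as a reason for conditional wording, but it does not close the gap. The content of the follow-up form is not given, Section 11.4 ties data entry to the calendar, and shifted columns do not explain a row that is absent.

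Three stronger readings are tempting, and the documents do not support them.
- A reader might infer that the endpoint will be largely unobserved. That depends on a gap the documents do not state; if therapy usually starts at progression, most events are captured.
- A reader might infer that 6 × 1.5 = 9 of 46 men (20%) would lack the six-month primary endpoint at month 36. Section 8.3 sets the final analysis by six months' follow-up for everyone, and Section 3.2 gives only an approximate date, so this loss does not occur under the operative rule.
- A reader might infer that this endpoint is the trial's test of whether pacritinib delays androgen deprivation. Section 1.1 motivates a non-hormonal option without mentioning the endpoint, which is one of five secondary endpoints and is summarised descriptively in a single arm.

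**Conclusion.** The point holds as a risk that should be corrected, not as a predicted failure. No item for subsequent therapy or its start date is named beyond 30 days after the last dose. Followed literally, the plan would censor later starters informatively and bias the median upward. Capture ranges from 82–94% with no gap to 17–19% at an assumed three-month median gap, before any loss from an early close. These figures assume exponential times, treatment to progression or 24 months, and the concomitant-medication record as the only source. Men stopped early for toxicity are not modelled and could lower capture.

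The duration conflict needs no assumption about the gap: no reading of 36 months accommodates two years of follow-up from the end-of-treatment visit. It is a contradiction to be reconciled, not evidence of a planned cut-off. Neither issue affects the primary decision rule.

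**What to change.** 1. Add a Study Calendar row for subsequent antineoplastic therapy (type and start date) at the end-of-treatment visit and every existing six-monthly follow-up visit, with a matching CRF field kept separate from the 30-day concomitant-medication window. Ask for the actual start date, so that six-monthly visits do not blur the timing.
2. In Section 8.5 or 8.10, state the endpoint's time origin, and censor at the last contact at which therapy status was ascertained.
3. Reconcile the Protocol Summary, calendar footnote 3, Section 3.2 and Section 8.3. State primary completion (six months after the last subject starts) separately from study completion (end of the last subject's follow-up, or a stated earlier cut-off with this endpoint reported as truncated there).

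The cost is one extra field at visits already scheduled and a longer stated study duration. No visits or patients are added. Under the same assumptions, recording through the full follow-up would observe 95–99% of events at a three-month median gap, and at least 71% even at twelve months.
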